### **3.2 Demographics and Baseline Characteristics**

The following variables will be summarized for the Full Analysis Set.

- Demographics (age, sex, race, and ethnicity) and Physical Characteristics (weight in kg, height in cm, and body mass index (BMI) in kg/m^2)
  - Age will be calculated as the difference between the informed consent date and the birth date, rounded to the nearest year. (The corresponding SAS function is 'yrdif' with the 'AGE' option, rounded to the nearest year.)
  - Subjects in more than one race category will be categorized as 'Multiple'.
  - Weight measurements in pounds will be converted to kilograms using: 1 pound = 0.453592 kg
  - Height measurements in inches will be converted to centimeters using: 1 inch = 2.54 cm
- Number and percent of subjects by primary cancer diagnosis
- Number and percent of subjects having history of systemic therapy, radiation, surgery, transplant, and/or transfusion
- Number and percent of subjects by baseline Eastern Cooperative Oncology Group (ECOG) performance status
- Number and percent of subjects having Medical Dictionary for Regulatory Activities (MedDRA) coded medical history conditions by System Organ Class (SOC) and Preferred Term (PT).

### **3.3 Protocol Deviation**

Major protocol deviations will be summarized for the full analysis set. In addition, a listing of Major protocol deviations and a listing of protocol deviations related to COVID-19 will be provided.

### **3.4 Extent of Exposure**

The analysis population for exposure is the Safety Analysis Set by:

- Initial assigned dose levels or initial assigned dosing schedules (in the case of Part 4 biweekly) for Part 1 and Part 4 (Dose Escalation cohorts)
- Monotherapy or combination therapy for Part 2 and Part 3

For each study drug administered (TTI-621, nivolumab, and rituximab), the following measures of exposure will be summarized.

- Total number of doses received
- Cumulative dose (in mg/kg for TTI-621, mg for nivolumab, and mg/m^2 for rituximab)
- Average dose (in mg/kg for TTI-621, mg for nivolumab, and mg/m^2 for rituximab) = Cumulative dose / total number of doses received
- Duration of treatment (days) = Date of last dose date – date of first dose + n
  - where n is as follows, for the respective study drug:
    - For TTI-621 for subjects not assigned to Part 4 Q2W, n=7
    - For TTI-621 for subjects assigned to Part 4 Q2W, n=14
    - For Rituximab, n=7
    - For Nivolumab, n=14

The following categorical summaries of exposure also will be provided for each study drug administered (TTI-621, nivolumab, and rituximab).

- Number and percent of subjects having a dose interruption
- Number and percent of subjects by reason for dose interruption
- Number and percent of subjects having a dose reduction
- Number and percent of subjects by reason for dose reduction

For the purposes of these analyses, dose interruption generally indicates all instances in which a subject experiences a delay in the scheduled administration of study drug and the corresponding fields are populated on the respective treatment CRF form.

For the purposes of these analyses, dose reduction generally indicates all instances in which the subject is treated at a lower dose level different to their extant assigned dose level and when the corresponding fields are populated on the respective treatment CRF form.

In subjects who received intrapatient dose escalation (IDE), the range of weeks at each dose level of TTI-621 will be presented. Details are as follows:

- Subjects will be considered as having dose escalated if their C1D1 actual dose level is as assigned and they experience at least one instance of dose increase such that their actual dose level is greater than their assigned dose level.
- Summarization will be presented by maximum TTI-621 dose level administered.
- The range of weeks at each dose counts the number of weeks the subject was actually treated with TTI-621 at the given dose level.

Descriptive statistics for the compliance rate will be provided.

The compliance rate for each subject will be calculated as follows.

$$\text{Compliance rate} = 100 * \frac{\text{Cumulative dose of study drug received}}{\text{Cumulative dose of study drug planned}}$$

where *Cumulative dose of study drug received* is the total sum of the Dose per Administration field per subject and *Cumulative dose of study drug planned* is the total sum of the Planned Dose per Administration field per subject captured on or derived

from the corresponding study drug treatment CRF. The unit of cumulative dose is mg/kg for TTI-621, mg for nivolumab, and mg/m^2 for rituximab, respectively.

### **3.5 Safety Analyses**

The analysis population for safety is the Safety Analysis Set by:

- Initial assigned dose levels or initial assigned dosing schedules (in the case of Part 4 biweekly) for Part 1 and Part 4 (Dose Escalation cohorts)
- Monotherapy or combination therapy for Part 2 and Part 3

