Pharmacodynamic measurements and biomarkers will be summarized using summary statistics and may be displayed graphically as appropriate. Subgroup analyses, which will be pre-specified in the SAP, may be conducted in the expansion phase of the study to explore the relationship between measures of anti-tumor activity and selected baseline biomarkers.

*Phase 1b Part 3-Specific Analyses*

Each of the 2 additional cohorts (CTCL and PTCL) will be evaluated separately for the potential to be further studied using the Simon 2-stage design. For the first stage, a total of 18 response-evaluable subjects will be reviewed in each cohort; if 2 or fewer responders are observed, enrollment in the respective cohort will be terminated. Otherwise, enrollment will continue to the second stage and an additional 17 subjects will be enrolled for a total of 35 response-evaluable subjects per cohort. At the end of the second stage, if 6 or fewer responders per cohort are observed, the drug will be rejected for further testing in this indication. The safety and efficacy assessments outlined above will be summarized for each cohort separately. If more than the required number of response-evaluable patients are available (i.e., >18 or >35), the first 18 or 35, respectively, would be used.

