Thrombocytopenia/platelet count decreased were the most frequently reported  $\geq$ Grade 3 related TEAEs, occurring in 19/179 (11%) and 16/179 (9%) of subjects respectively. Thrombocytopenia/platelet count decreased occurred within 24 hours following infusion in majority of patients exposed to IV administration of TTI-621. Reduced platelet counts appeared transient and generally recovered within a week prior to the next dosing. Overall, pre-infusion platelet counts remained stable over the course of the study and no clinical sequela was observed (See [Section 1.8.4](#)).

Grade 3/4 cytopenias, including decreased monocytes, neutrophils, and lymphocytes, were observed and reported as laboratory abnormalities as well as TEAEs.

Treatment-related, Grade 3 or higher anemia was reported in 11 subjects receiving IV TTI-621. All events occurred in subjects with primary hematologic malignancies in which anemia is frequently caused by the malignancy itself (AML/MDS/MPN). No serious events of anemia were reported and anemia did not appear to be associated with increased destruction of erythrocytes.

See [Section 9.5](#) for further details of anticipated risks and AEs of special interest.

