## **8.4 Statistical Methods**

The statistical analyses performed for this study will be presented by study phase. For the escalation phase, tabulations will be provided by dose cohort and overall. For the expansion phase, tabulations will be provided by disease cohort and overall. Some analyses may be performed based on the dose escalation and expansion phases combined.

The statistical analyses will be performed using SAS® version 9.2 or later (SAS Institute Inc, Cary NC). Programming specifications will be prepared which describe the datasets and variables created for this study. The datasets will be prepared using the most recent version of CDISC's Study Data Tabulation Model (SDTM) and Analysis Dataset Model (ADaM). The source SDTM and ADaM datasets from which a statistical analysis is performed (including interim safety reviews) will be archived with the Sponsor.

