#### **8.4.2 Demographics and Baseline Characteristics**

Descriptive summaries of demographic and baseline characteristics for all enrolled subjects will be tabulated by study phase – overall and by dose for Phase 1a (dose escalation/dose finding stage) and overall and by disease cohort for the additional subjects. Each cohort to be presented will be defined in the SAP to provide guidance for the tabulation summaries.

This format of presentation will be used for the safety, efficacy, PK, immune response and biomarker presentations.

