### **3 Analyses and Summaries**

The statistical analyses performed for this study will be summarized by the following unless indicated otherwise:

- Initial assigned dose levels or initial assigned dosing schedules (in the case of Part 4 biweekly) for Part 1 and Part 4 (Dose Escalation cohorts)
- Monotherapy or combination therapy for Part 2 and Part 3
- Indication within monotherapy and by combination therapy for Part 2 and Part 3

The statistical analyses will be performed using SAS® version 9.2 or later (SAS Institute Inc., Cary NC). Programming specifications will be prepared which describe the datasets and variables created for this study. The datasets will be prepared using the most recent version of the Clinical Data Interchange Standards Consortium (CDISC) Study Data Tabulation Model (SDTM) and Analysis Dataset Model (ADaM). The source SDTM and ADaM datasets from which a statistical analysis is performed (including interim safety reviews) will be archived with the Sponsor.

The following data conventions will be employed in the study.

- Summary tables for continuous variables will contain the following statistics: N (number in population); n (number with data); mean; standard deviation; median; minimum; and maximum. Selected tables also may include 2-sided 95% confidence intervals (CIs) on the mean, calculated using a t-distribution approximation.
- Summary tables for categorical variables will include: N (number in denominator); n (number in numerator); and percent. Selected tables also may include 2-sided 95% CIs for the percent, calculated using the Clopper-Pearson method.
- Data from all study centers will be pooled for all analyses.
- The baseline value for a given parameter is the last value prior to the time of the first dose. A value is considered to be post-baseline if it is obtained after the time of the first dose.
- Study Day is defined as Calendar Date – Date of First Treatment + 1 if the calendar date is on or after the date of the first treatment, and Calendar Date – Date of First Treatment if the calendar date is before the date of the first treatment.
- Partial dates will be displayed as partial dates in listings and missing dates will be displayed as missing. The corresponding Study Day for partial or missing dates will be displayed as missing in listings.
- Unless specifically noted later in this SAP, missing data will not be imputed.

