#### **3.5.1 Adverse Events**

Adverse events (AEs) are recorded by the sites in the CRFs according to CTCAE v4.03. The CRFs also identify the following characteristics of each AE:

- The start date and end dates of the AE
- The outcome of the AE
- The severity grade of the AE
- The relationship of the AE to study treatment TTI-621 (related or unrelated)
- The relationship of the AE to rituximab or nivolumab in the combination therapy, if applicable (related or unrelated)
- Whether the AE was a Dose Limiting Toxicity (DLT) for dose escalation portion (Part 1 and non-Q2W Part 4)
- Whether the AE was a Serious Adverse Event (SAE)
- Study treatment actions (for any administered anti-cancer therapy) taken in response to the AE
- Other actions taken in response to the AE

Verbatim AE terms will be coded into preferred term (PT) and system organ class (SOC) by Pfizer using the most recent version of MedDRA available at time of analysis.

Treatment-emergent adverse events (TEAEs) are defined as AEs having a start date on or after the date of the first dose of study drug and on or before the date of the last dose of study drug plus 30 days. AEs starting more than 30 days after the final study drug administration will be included in listings, but not in summary tables. AEs outside the on-treatment period will be flagged in the listings.

Adverse events of special interest include the following:

- Thrombocytopenia: Haematopoietic thrombocytopenia – SMQ Broad
- Other Cytopenias:
  - Haematopoietic cytopenias affecting more than one type of blood cell – SMQ- Broad
  - Haematopoietic leukopenia – SMQ - broad and narrow
- Anemia: Haematopoietic erythropenia – SMQ – broad
- Hemorrhage: Haemorrhage terms (excl laboratory terms) – SMQ narrow
- Infusion related reactions
- ALT/AST elevations

An overview summary will be provided of the number and percentage of subjects in each of the following categories as applicable:

- at least one TEAE
- at least one TEAE of Grade  $\geq$  3

- at least one related TEAE
- at least one related TEAE of Grade  $\geq 3$
- at least one serious TEAE
- at least one related serious TEAE
- at least one TEAE leading to drug withdrawal of TTI-621
- at least one TEAE leading to drug withdrawal of rituximab
- at least one TEAE leading to drug withdrawal of nivolumab
- at least one related TEAE leading to drug withdrawal of TTI-621
- at least one related TEAE leading to drug withdrawal of rituximab

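### SAP 3.5 and 3.4 leave out the by-indication and by-combination grouping for Parts 2 and 3, so the adverse event tables as written lose the protocol's by-cohort layout

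*SAP*

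**What the plan says.** SAP 3 lists three grouping levels and states that analyses "will be summarized by the following unless indicated otherwise". The first covers dose levels and schedules in Parts 1 and 4. The second separates monotherapy from combination therapy in Parts 2 and 3. The third is "Indication within monotherapy and by combination therapy for Part 2 and Part 3".

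SAP 3.5 restates the list for safety with only the first two levels; its entry for the expansion parts is "Monotherapy or combination therapy for Part 2 and Part 3". SAP 3.4 (exposure) has the same two-level list. SAP 3.5.4 (prior therapies) keeps all three levels, and SAP 3.7 (efficacy) uses the third as its only grouping for Parts 2 and 3.

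Protocol 8.4 says "For the expansion phase, tabulations will be provided by disease cohort and overall", and the synopsis repeats the rule under Safety Analyses. Protocol 8.4.2, after setting out tabulation overall and by disease cohort, adds "This format of presentation will be used for the safety, efficacy, PK, immune response and biomarker presentations". For the CTCL and PTCL cohorts of Part 3, the synopsis says "The safety and efficacy assessments outlined above will be summarized for each cohort separately".

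**The concern.** Incidence and severity of adverse events is the primary endpoint of Parts 2 and 3. Safety in combination with other anticancer agents is a stated objective, and SAP 1.2.3 frames it partner by partner: one cohort to characterise the rituximab combination, another to characterise the nivolumab combination. One combined column characterises neither. Protocol 1.7 shows that safety in a single combination has already mattered: after a Grade 3 gastrointestinal bleed, the TTI-621 starting dose used with rituximab was lowered.

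Disease mix is a second issue. Part 2 monotherapy spans AML, MDS and MPN as well as lymphomas, myeloma and small cell lung cancer. Where the underlying malignancy itself produces cytopenias, a rate over the whole group depends partly on who was enrolled. Part 3 has a similar gap, because CTCL and PTCL would share one group although the protocol wants them apart.

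**Working it through.** The documents give no figure to reproduce here. The check is a comparison of text, followed by an illustration of size.

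**Step 1: which level applies where (Parts 2 and 3).**

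| SAP section | Monotherapy vs combination | Indication / each combination |
|---|---|---|
| 3 (default) | yes | yes |
| 3.4 Exposure | yes | no |
| 3.5 Safety | yes | no |
| 3.5.4 Prior therapies | yes | yes |
| 3.7 Efficacy | no | yes |

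Each of these sections restates its own list, so an omission reads as an override of the default. SAP 3 treats division by combination as a separate, finer level. The coarser entry therefore most naturally means a single combination group.

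**Step 2: what partner or disease detail survives.** The CRF records attribution to rituximab or nivolumab, and all adverse events are listed. The overview and the SOC/PT tables have rows such as "at least one TEAE leading to drug withdrawal of nivolumab", but no denominator is stated for them. Antidrug antibodies (3.5.6) are by cohort. TFLs are separate for each part (1.2.6), so pooling is within a part. None of this gives the incidence of TEAEs, Grade 3 or higher events, serious events or events of special interest by partner or by disease.

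**Step 3: possible size.** Inputs: up to 15 nivolumab and up to 40 rituximab subjects (expansion cohort table in the protocol synopsis). Event rates are assumed.

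Pooled rate = (15 × p_niv + n_rit × p_rit) / (15 + n_rit)

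- Nivolumab-only event, p_niv = 20%, p_rit = 0, n_rit = 40: 3/15 = 20.0% (95% Clopper-Pearson CI 4.3% to 48.1%) prints as 3/55 = 5.5% (1.1% to 15.1%). The ratio is 55/15 = 3.7.
- p_niv = 20%, p_rit = 5%, n_rit = 40: (3 + 2)/55 = 9.1%. The ratio is 20/9.1 = 2.2.
- p_niv = 40%, p_rit = 10%, n_rit = 40: (6 + 4)/55 = 18.2%.
- Nivolumab-only event with fewer rituximab subjects: n_rit = 25 gives 3/40 = 7.5%; n_rit = 15 gives 3/30 = 10.0%.
- Rituximab-only event: 8/40 = 20.0% (9.1% to 35.6%) prints as 8/55 = 14.5% (6.5% to 26.7%). The ratio is 55/40 = 1.4.

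**Step 4: partner-drug rows.** If these rows used the pooled group as denominator, 15/55 = 27% of it would have received nivolumab and 40/55 = 73% rituximab.

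**The case against.** The strongest reply is that nothing has been dropped. SAP 3 sets a default, and 3.5 never says that the indication level is excluded. No sentence puts rituximab and nivolumab in one column, the overview rows are given only where applicable, and the table layouts are in a separate document that was not available. The protocol leaves final details and cohort definitions to the SAP and allows some safety analyses on all treated subjects combined. The SAP serves an abbreviated report, listings remain available, and 3.4 already summarises exposure drug by drug.

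Part of this stands. Pooling is the natural reading, not an explicit instruction, and some output under 3.5 does keep cohort or partner detail. But if the default was meant to survive, 3.5 should say so, because a programmer working from 3.5 would not build those columns. Latitude for some combined analyses does not replace the by-cohort rule, and listings do not replace primary-endpoint tables. Drug-by-drug exposure still leaves TTI-621 exposure pooled across the two combinations.

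A reader might infer three stronger things that the documents do not support:

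- **That most of the pooled group never received the drug named in each partner-drug row.** At planned maxima this is true for nivolumab (40 of 55 would not have received it) and false for rituximab (40 of 55 would). The denominator is not stated in any case.
- **That monotherapy cytopenia rates mainly reflect marrow disease.** Protocol 1.7 ties only treatment-related Grade 3 or higher anemia (11 subjects) to diseases such as AML, MDS and MPN, and says this of all the events. Protocol 9.5 says only most frequently, and lists AML, MDS, myeloma and advanced Hodgkin lymphoma. Thrombocytopenia is described as an acute post-infusion effect in most exposed subjects, and it was already seen in the escalation phase, which enrolled lymphoma only.
- **That nivolumab toxicity will be understated 3.7-fold.** That figure requires no events in any rituximab subject at full planned enrolment. Both cohorts receive TTI-621, so many toxicities would be shared.

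**Conclusion.** The point holds. As written, SAP 3.5 and 3.4 omit a grouping level that the SAP defines and uses elsewhere. The adverse event tables therefore depart, without a stated reason, from the protocol's tabulation by disease cohort and from its separate reporting of CTCL and PTCL. This affects the primary endpoint of Parts 2 and 3 and should be corrected before the tables are produced.

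The size cannot be fixed from the documents. At planned maxima, a 20.0% nivolumab-only rate would print as 5.5%, which is the upper bound of the dilution; with 5% in rituximab subjects it would print as 9.1%. These figures rest on assumed event rates, on planned rather than actual enrolment, and on reading the combination entry as one group. Disease mix can confound cytopenia rates, most clearly for Grade 3 or higher related anemia, but the documents do not show how far, and protocol 1.7 and 9.5 differ on the diseases involved.

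**What to change.** Add the third SAP 3 grouping to SAP 3.5 and 3.4. State that rituximab and nivolumab have separate columns, that monotherapy is shown by disease cohort (CTCL and PTCL separately in Part 3), and that the pooled column stays as the overall. For rows on withdrawal, interruption or reduction of a partner drug, define the denominator as the subjects who received that drug. If pooling is intended, record it in the SAP as a departure from protocol 8.4 and 8.4.2, with the reason.

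The grouping variables are already used in 3.5.4 and 3.7, so the cost is SAP wording and additional columns. Percentages in small cohorts will be imprecise, as the interval of 4.3% to 48.1% around 3/15 shows, so counts should be printed beside them.

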#### **3.5.1 Adverse Events**

Adverse events (AEs) are recorded by the sites in the CRFs according to CTCAE v4.03. The CRFs also identify the following characteristics of each AE:

- The start date and end dates of the AE
- The outcome of the AE
- The severity grade of the AE
- The relationship of the AE to study treatment TTI-621 (related or unrelated)
- The relationship of the AE to rituximab or nivolumab in the combination therapy, if applicable (related or unrelated)
- Whether the AE was a Dose Limiting Toxicity (DLT) for dose escalation portion (Part 1 and non-Q2W Part 4)
- Whether the AE was a Serious Adverse Event (SAE)
- Study treatment actions (for any administered anti-cancer therapy) taken in response to the AE
- Other actions taken in response to the AE

Verbatim AE terms will be coded into preferred term (PT) and system organ class (SOC) by Pfizer using the most recent version of MedDRA available at time of analysis.

Treatment-emergent adverse events (TEAEs) are defined as AEs having a start date on or after the date of the first dose of study drug and on or before the date of the last dose of study drug plus 30 days. AEs starting more than 30 days after the final study drug administration will be included in listings, but not in summary tables. AEs outside the on-treatment period will be flagged in the listings.

Adverse events of special interest include the following:

- Thrombocytopenia: Haematopoietic thrombocytopenia – SMQ Broad
- Other Cytopenias:
  - Haematopoietic cytopenias affecting more than one type of blood cell – SMQ- Broad
  - Haematopoietic leukopenia – SMQ - broad and narrow
- Anemia: Haematopoietic erythropenia – SMQ – broad
- Hemorrhage: Haemorrhage terms (excl laboratory terms) – SMQ narrow
- Infusion related reactions
- ALT/AST elevations

An overview summary will be provided of the number and percentage of subjects in each of the following categories as applicable:

- at least one TEAE
- at least one TEAE of Grade  $\geq$  3

- at least one related TEAE
- at least one related TEAE of Grade  $\geq 3$
- at least one serious TEAE
- at least one related serious TEAE
- at least one TEAE leading to drug withdrawal of TTI-621
- at least one TEAE leading to drug withdrawal of rituximab
- at least one TEAE leading to drug withdrawal of nivolumab
- at least one related TEAE leading to drug withdrawal of TTI-621
- at least one related TEAE leading to drug withdrawal of rituximab
- at least one related TEAE leading to drug withdrawal of nivolumab
- at least one TEAE leading to drug interruption of TTI-621
- at least one TEAE leading to drug interruption of rituximab
- at least one TEAE leading to drug interruption of nivolumab
- at least one TEAE leading to drug reduction of TTI-621
- at least one TEAE leading to drug reduction of rituximab
- at least one TEAE leading to drug reduction of nivolumab
- at least one TEAE leading to death
- at least one related TEAE leading to death
- at least one TEAE of special interest Thrombocytopenia SMQ (broad)
- at least one TEAE of special interest Other Cytopenias SMQ (broad)
- at least one TEAE of special interest Anemia SMQ (broad)
- at least one TEAE of special interest Hemorrhage SMQ (narrow)
- at least one TEAE of special interest Infusion related reactions
- at least one TEAE of special interest ALT/AST elevations

For summaries of the number and percent of subjects by SOC and/or PT, subjects reporting multiple TEAEs within the same SOC/PT will be counted only once for that SOC/PT. SOCs and PTs in summaries will be displayed in order of decreasing total frequency of TEAEs.

Summaries of TEAEs and serious TEAEs by SOC, PT, and severity grade will be presented. For this summary, subjects reporting multiple TEAEs within the same SOC or PT will be counted only once for that SOC or PT using the highest severity grade.

Summaries of TEAEs and serious TEAEs by SOC, PT, and relationship to study drug will be presented. For this summary, subjects reporting multiple TEAEs within the same SOC or PT will be counted only once for that SOC or PT using the strongest causal relationship.

Separate summaries by SOC and PT will be presented for the following types of AEs:

- TEAEs by maximum severity grade
- TEAEs of any grade and Grade  $\geq 3$  severity
- Related TEAEs by maximum severity grade
- Related TEAEs of any grade and Grade  $\geq 3$  severity
- All serious TEAEs
- Related serious TEAEs
- DLTs (for Part 1 and non-Q2W Part 4 dose escalation cohorts only)
- TEAEs leading to drug withdrawal of TTI-621
- TEAEs leading to drug withdrawal of rituximab
- TEAEs leading to drug withdrawal of nivolumab
- Related TEAE leading to drug withdrawal of TTI-621

- Related TEAE leading to drug withdrawal of rituximab
- Related TEAE leading to drug withdrawal of nivolumab
- TEAEs leading to drug interruption of TTI-621
- TEAEs leading to drug interruption of rituximab
- TEAEs leading to drug interruption of nivolumab
- TEAEs leading to drug reduction of TTI-621
- TEAEs leading to drug reduction of rituximab
- TEAEs leading to drug reduction of nivolumab
- TEAEs leading to death
- Related TEAEs leading to death

The following TEAEs of special interest will be summarized by SMQ and PT as applicable:

- Thrombocytopenia (broad)
- Other Cytopenias (broad)
- Anemia (broad)
- Hemorrhage (narrow)

The following TEAEs of special interest will be summarized by PT:

- Infusion related reactions
- ALT/AST elevations

The following listings will be presented:

- All AEs (including whether or not the AE is defined as a TEAE, as well as other identifying characteristics from the AE CRF)
- All DLTs
- AEs leading to death
- COVID-19 related AEs

